Analyses for Specific Aim 1: Hypothesis: Greater ED and WMH will be associated with smaller differences in patient expectancy and antidepressant outcome between the open and placebo-controlled conditions. All tests will be two-sided:  $\alpha=0.05$ , intent-to-treat, with data included for all patients with  $\geq 1$  post-baseline assessment. The primary outcome measure of expectancy (items 2 and 4 of the CES) and antidepressant outcome (24-item HRSD) will be collected at baseline and at weeks 1 through 8. Analysis for expectancy will include all randomized individuals (n=130), analysis for HRSD will drop the n=10 individuals who receive placebo to strictly compare the antidepressant drug outcome of open label vs. double-blind. The hypothesis is addressed by testing the 3-way interaction ( $\beta_8$  in Model 1 below) between baseline ED/WMH, time, and treatment condition. 'ED/WMH' denotes our intention to analyze the effects of ED and WMH individually as well as in combination. The longitudinal mixed effect model (Model 1) will be used where  $Y_{ij}$  is the expectancy or HRSD score for subject  $i$  at  $t_j$  week,  $t_j=1,2,\dots,8$ ,  $y_{i0}$  is expectancy or HRSD at baseline,  $I_i^{TRT}$  is the indicator variable for randomized condition (open label vs. double-blind),  $ED/WMH_i$  is the baseline measure of ED/WMH (see section 3.3.B.6),  $X_i$  includes the randomization stratification variable (i.e., age) and any baseline covariates exhibiting imbalance after randomization,  $b_i$  is a random intercept to account for repeated measures across time within patient, and  $g(t_i)$  is a general function of time to allow for non-linear time trends. We will determine the best way to model  $g(t_i)$  by comparing BIC fit criteria across models including linear, cubic splines, or categorical (i.e., dummy variable) time effects. Model 1 will be fit using PROC GLIMIX in SAS. A significant interaction of  $g(t_i) * I_i^{TRT} * ED/WMH_i$  (corresponding to rejecting the null hypothesis that  $\beta_8 = 0$ ) indicates that the effect of randomized condition on the outcome over time is different by baseline ED/WMH. Because this interaction effect is a function of continuous time and ED/WMH, interpretation will be facilitated by forming contrasts at different fixed values of time (e.g., early vs. late, week 1 vs. week 8) and ED/WMH severity (low vs. moderate vs. high defined by tertiles of baseline ED/WMH distributions). Model 1 will also be used to analyze secondary measures of expectancy (QIDS-SR Expectancy Version) and to test moderator effects of secondary measures of ED and WMH (see sections 3.3.B.5-6.)

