
Analyses for Specific Aim 2: Hypothesis: ED and WMH will be associated with decreased change in depressive symptoms, and this association will be mediated by a decreased contribution of expectancy to antidepressant outcome. The first part of this hypothesis will be tested using a longitudinal mixed effect for HRSD scores as in Model 1 but only including predictors that do not involve randomized condition, i.e.  $\beta_0, \beta_1, \beta_2, \beta_6, \beta_9$ . The tests of interest are the main effect for ED/WMH and its interaction with time (i.e.  $\beta_4$  and  $\beta_6$ ). After having established an overall effect of ED and/or WMH on depression outcome (i.e., HRSD), we will test

$$\text{MODEL 1: } Y_{ij} = \beta_0 + \beta_1 y_{i0} + \beta_2 g(t_j) + \beta_3 I_i^{TRT} + \beta_4 ED/WMH_i + \beta_5 g(t_j) * I_i^{TRT} + \beta_6 g(t_j) * ED/WMH_i + \beta_7 I_i^{TRT} * ED/WMH_i + \beta_8 g(t_j) * I_i^{TRT} * ED/WMH_i + \beta_9 X_i + b_i + \epsilon_{ij}$$

[figure not shown]

Figure 5. Mediation of the relationship between ED/WMH and antidepressant outcome by a loss of expectancy effects.

$\beta_4$ ,

expectancy as a mediator of the relationships (see Figure 5). To be a mediator we must establish that expectancy is affected by ED/WMH and that it influences antidepressant outcome controlling for ED/WMH. In order to ensure time order of the mediator (expectancy) occurring prior to the depression outcome (HRSD), we will use early change in expectancy (i.e., from baseline to week 1) as the primary measure for the mediator. A model with week 1 expectancy as the outcome and ED/WMH as the primary predictor, controlling for baseline covariates, will be used to estimate path a in Figure 5. To estimate path b in Figure 5, the same longitudinal mixed effect model described above with the addition of week 1 expectancy as a predictor will be used. The mediation effect is estimated by taking the product of the estimates for a and b and using the bootstrap method to obtain standard errors, confidence intervals, and the test for statistical significance. Recent developments in mediation analysis suggest the need for sensitivity analyses to explore potential impact of unmeasured confounders. We will perform these sensitivity analyses with the new mediation R package that provides a range of plausible results that may have been obtained under different assumptions about unmeasured confounders.

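### The planned baseline adjustment does not reach the Aim 2 ED/WMH × time test (β6), which is biased if ED/WMH correlates with baseline HRSD and the baseline slope also changes over weeks 1-8

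*SAP*

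**What the plan says.** The relevant text is in the SAP, Analyses for Specific Aim 1 and Analyses for Specific Aim 2.

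- **Outcome times.** Expectancy and HRSD "will be collected at baseline and at weeks 1 through 8". In Model 1 the outcome runs over weeks 1-8, and the baseline score y_i0, which "is expectancy or HRSD at baseline", is a covariate.
- **Time terms.** The function g(t) "is a general function of time to allow for non-linear time trends". BIC chooses its shape (linear, cubic splines or categorical). In the equation g(t) multiplies treatment, ED/WMH and their product. It does not multiply y_i0, which appears only as β1·y_i0.
- **Other covariates.** X_i holds age and "any baseline covariates exhibiting imbalance after randomization", as main effects.
- **Random effects.** The only one is b_i, which "is a random intercept to account for repeated measures across time within patient".
- **Reuse in Aim 2.** HRSD is modelled "as in Model 1 but only including predictors that do not involve randomized condition". "The tests of interest are the main effect for ED/WMH and its interaction with time", that is β4 and β6. Mediation by expectancy is tested once an overall effect is established.

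Neither document adds a baseline-by-time term or a sensitivity analysis for one.

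**The concern.** A single β1 assumes that a point of baseline HRSD predicts week 1 and week 8 equally well. If that is untrue, the reduced Aim 2 model has only one patient-level covariate that can change its effect over time, and that is ED/WMH. The part of the changing baseline effect that is linearly related to ED/WMH then appears in β6. ED/WMH is not randomised, so nothing in the design makes its correlation with baseline HRSD zero.

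β6 is one of two tests meant to establish that ED/WMH worsens outcome, and the mediation analysis follows from that result. Score ED/WMH so that higher is worse; Hypothesis 2 then predicts a positive β6. With a fading baseline slope, a positive correlation pushes β6 down and hides non-response. A negative correlation pushes it up and produces apparent non-response.

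**Working it through.** **Plan's own figure.** There is none. The documents give no power, SD, weekly baseline slope or ED/WMH-baseline correlation for this test.

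**Inputs from the documents.** Weeks 1-8, two-sided α=0.05, random intercept. N=120 is 130 − 10 placebo; this is stated for the Aim 1 HRSD analysis and assumed here for Aim 2. Dropout is 1 − 99/138 = 28% (protocol, Overall Progress).

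**Assumed inputs.** Baseline SD 5, residual SD 4, intercept SD 4, ED/WMH standardised, no true ED/WMH effect given baseline. Baseline slope γ(t) is linear in week. ρ is the correlation of ED/WMH with baseline HRSD.

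**Step 1: what β6 estimates.** With complete data and linear time, a random-intercept model estimates time interactions from within-patient contrasts. β6 is then the regression of each patient's week 1-8 slope on ED/WMH alone. The term β1·y_i0 is constant within a patient and drops out.

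**Step 2: size of the bias.** Bias in β6 per week = [(γ8 − γ1)/7] × ρ × SD(y0)/SD(ED). For γ from 0.8 to 0.4 and ρ=0.3: (−0.4/7) × 0.3 × 5 = −0.086 per week per SD of ED/WMH. Over the 7 weeks from week 1 to week 8 this is −0.6 HRSD points.

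**Step 3: rejection at nominal 5%** (2,000 runs per row, complete data).

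| γ week 1 → 8 | ρ | Bias per week | As planned | With y_i0 × t |
|---|---|---|---|---|
| 0.6 → 0.6 | −0.3 to 0.3 | 0 | 4.4-5.3% | 4.2-5.2% |
| 0.8 → 0.6 | 0.1 | −0.014 | 6.8% | 5.0% |
| 0.8 → 0.6 | 0.2 | −0.029 | 8.9% | 5.0% |
| 0.8 → 0.6 | 0.3 | −0.043 | 12.8% | 5.0% |
| 0.8 → 0.4 | 0.1 | −0.029 | 9.6% | 4.6% |
| 0.8 → 0.4 | 0.2 | −0.057 | 20.2% | 5.1% |
| 0.8 → 0.4 | 0.3 | −0.086 | 35.1% | 5.3% |
| 0.8 → 0.4 | −0.3 | +0.086 | 32.8% | 5.0% |

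With 28% dropout (ρ=0.3, 0.8 → 0.4, 150 runs), the planned model gives β6 of −0.096 and 36% rejection; with the term, −0.012 and 6%. With residual SD 3.5, intercept SD 4.5 and complete data, the 0.8 → 0.4 rows become 22% (ρ=0.2) and 40% (ρ=0.3). With residual SD 4.5, intercept SD 5 and dropout, the ρ=0.2 figure is 15%.

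**Step 4: masking.** Take a true β6 of 0.15 points per week per SD, γ from 0.8 to 0.4, residual SD 3.5, intercept SD 4.5 and complete data. The planned model targets 0.15 − 0.057 = 0.093 at ρ=0.2 and 0.15 − 0.086 = 0.064 at ρ=0.3. Power is 46% as planned against 84% with the term (ρ=0.2), and 26% against 81% (ρ=0.3).

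**Step 5: β4.** Patient means are adjusted correctly, so with complete data the ED/WMH effect at the mean week, β4 + 4.5·β6, is unbiased. With time in weeks from baseline, β4 shifts by −4.5 × (−0.086) = +0.39 at ρ=0.3. The run with dropout gave +0.37. The shift depends on the time origin, which the SAP does not state. The β4 rejection rate in those 150 runs was 10% with fading and 9% without, too close to show inflation of that test.

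**Step 6: other terms.** Adding age × t left β6 rejection at 33% against 34% (ρ=0.3, 0.8 → 0.4). For β8, rejection was 4.6-10.4% under fading, with no trend in ρ.

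**The case against.** **Correlation alone does not bias the test.** A reader might infer that β6 is biased whenever ED/WMH correlates with baseline severity. The first row of the table shows otherwise: with a constant slope, rejection stays near 5% at every ρ. The documents show neither a changing slope nor a correlation. The protocol's Background describes lesions as producing both depressive symptoms and ED, and the dose increases at week 4 depend on current symptoms, so both conditions are plausible. Neither is demonstrated. The HRSD entry threshold of 16 restricts the baseline range, which would tend to weaken the correlation; the simulations ignore this. This objection stands, and it is why the point is conditional.

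**β6 can be read as unadjusted.** Hypothesis 2 speaks of an association with change. Without the extra term, β6 is still the association of ED/WMH with the week 1-8 slope. That is fair, and the bias exists only for an effect conditional on baseline. But the plan puts y_i0 in the model, which suggests that the conditional effect is intended.

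**The rates depend on the covariance structure.** With patient-level slope SD 0.5-0.8 and only a random intercept fitted, rejection stays at about 10-22% even with y_i0 × t included. When slope variation is also modelled (SD 0.8), the model without the baseline term rejects 5.7% at ρ=0.2 with mild fading and 15% at ρ=0.3 with strong fading. The bias itself is unchanged; the larger standard error lowers the rejection rate. This stands as a limit on the rates above and as a separate problem.

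**Aim 1 and path b.** A reader might extend the point to β8 or to the mediation path from expectancy to HRSD. Randomisation keeps β8 essentially unbiased. In path b, week 1 expectancy enters with no stated time interaction, so with balanced data the extra term leaves its coefficient unchanged.

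**Conclusion.** The point holds in conditional form. The SAP text alone establishes that baseline HRSD has one constant coefficient and that, with complete data and linear time, it gives β6 no baseline adjustment. Bias in β6, with an opposite shift in β4, needs both a nonzero ED/WMH-baseline correlation and a baseline slope that changes over weeks 1-8. Only the part of that change linearly related to ED/WMH reaches β6; the rest goes to the residual.

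Across the assumed values the consequence runs from none to serious: about 5% rejection with no fading, and about 20-40% at correlations of 0.2-0.3 with the slope halving from 0.8 to 0.4. The upper figures assume residual SD 3.5-4 and no patient-level slope variation. The direction follows the sign of the correlation, so it cannot be called conservative in advance. Because the remedy is small and uses data already collected, the change should be made.

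**What to change.** Add y_i0 × g(t) to the reduced Aim 2 HRSD model, in the same g(t) form as the other time terms. Read β4 and β6 from that model, state the time origin at which β4 is interpreted, and report the ED/WMH-baseline HRSD correlation. In Model 1 for Aim 1 the term is optional.

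The cost is one sentence in the SAP and 1 df if g(t) is linear, or 7 if it is categorical (8 weeks less 1). No new data are needed. The protocol's status section says that only data analysis is ongoing, so the change should be dated and labelled as made at that stage, with the result as planned shown beside it. The term removes this bias only. It does not correct the separate inflation that arises if patients' slopes vary and only a random intercept is fitted.

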**Data analysis plan. Overview:**

The proposed trial will enroll 130 patients aged 60-90 years and randomize them to open label treatment with escitalopram

(n=60) vs. a double-blind

escitalopram-placebo trial (n=70, with n=60 to escitalopram and n=10 to placebo). Hence, participants in the double-blind condition will not know whether they are receiving drug or placebo. Patients will vary in their baseline severity of ED and WMH burden, which will be measured using the Stroop Color-Word Test and the Fazekas modified Coffey Rating Scale of anatomical MRI images, respectively. Specific Aim 1 focuses on determining whether differences in expectancy and depression outcomes found over time between the two randomized conditions are *moderated* by baseline ED and WMH measures (i.e., whether more severe ED and/or WMH are associated with smaller differences between the open and placebo-controlled conditions). Specific Aim 2 investigates whether poor antidepressant outcome (regardless of randomized condition) is associated with more severe baseline ED and WMH burden, and whether this association is *mediated* by decreased patient expectancy. In the Exploratory Aim, we are interested in using DTI to explore with greater anatomical precision the white matter damage associated with smaller differences in patient expectancy and antidepressant outcome between the open and placebo-controlled conditions.

Before the specific statistical techniques are applied, we will examine all variables at all time points for illegitimate values, outliers, and inconsistencies. The distribution of demographic variables, rater-administered and self-report measures will be examined and described in terms of means, standard deviations, minima, and maxima for continuous variables, and proportions for categorical variables. Missing data: We will make every effort to obtain all data. The longitudinal mixed modeling described below imputes unobserved time points using observed data from the individual combined with the overall trend. Inferences are valid if missing data are missing at random (MAR). MAR assumptions cannot be verified. A 2010 national expert panel recommended sensitivity analyses for the impact of missing data via pattern mixture models, which we will conduct (e.g., by investigating robustness of results to perturbations of assumed values for missing data within clinically plausible ranges).

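### Model 1 handles within-patient correlation by a random intercept alone, so its time-interaction tests (β8, β6) can exceed the stated 5% if patients' slopes vary beyond the modelled terms or weekly errors are serially correlated

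*SAP*

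**What the plan says.** The SAP, Analyses for Specific Aim 1, fits a longitudinal mixed model to expectancy and to HRSD at weeks 1 to 8, with the baseline value as a covariate and two-sided tests at 0.05. It says that b_i "is a random intercept to account for repeated measures across time within patient". The Model 1 equation, printed under Analyses for Specific Aim 2, ends in b_i + ε_ij. No random slope, residual correlation structure, robust variance or covariance-selection step appears in the analysis plan supplied.

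BIC has one task, to choose the mean function of time, "by comparing BIC fit criteria across models including linear, cubic splines, or categorical" effects. The Aim 1 hypothesis is tested by β8, the interaction of time, condition and ED/WMH. The ED/WMH notation "denotes our intention to analyze the effects of ED and WMH individually as well as in combination".

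For Aim 2 the HRSD model follows Model 1 "but only including predictors that do not involve randomized condition". "The tests of interest are the main effect for ED/WMH and its interaction with time", that is, β4 and β6.

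The only sensitivity analyses for the longitudinal models are in the Overview, which cites an expert panel that "recommended sensitivity analyses for the impact of missing data via pattern mixture models". Those vary the values assumed for missing data and leave the covariance as it is.

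**The concern.** Given baseline, a random intercept with unstructured-by-default independent errors implies the same between-patient spread at week 1 as at week 8, and the same correlation for weeks 1 and 2 as for weeks 1 and 8. In an eight-week antidepressant trial patients may well diverge over time, and adjacent weekly ratings may be more alike than distant ones.

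β8 and β6 are time interactions, which a random intercept does not protect. Any patient-to-patient difference in trajectory left in the data is counted as independent visit-level noise. Standard errors are then too small, and moderation by ED or WMH could be declared more often than the plan states.

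Two planned models might leave such variation over. A model with ED alone omits any effect of WMH on slope, and the reverse. The Aim 2 model omits any condition-by-time effect. Each matters only if the omitted factor does affect slope.

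**Working it through.** **Inputs from the SAP.** Weeks 1 to 8; two-sided 5%; HRSD n=120 (60 per condition); expectancy n=130 (60 and 70); time linear, spline or categorical.

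**Inputs assumed.** Slope SD, residual SD and AR(1) correlation. The documents give none of them.

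**Linear time, slopes varying.** Let r = slope SD / residual SD. Over weeks 1 to 8, Σ(t − 4.5)² = 42. The true variance of a patient's slope contrast is proportional to 1 + 42r². The random-intercept model estimates it by the average within-patient variance, proportional to 1 + (42/7)r² = 1 + 6r². So

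k = (1 + 42r²)/(1 + 6r²), and type I error = 2Φ(−1.96/√k).

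*The plan's own figure.* With r = 0, k = 1 and the error is 5.0%. Simulation at n=120 with a true random intercept only gave 4.2% to 4.9%, so the stated level holds under the plan's own assumption.

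| Slope SD (points/week) | k, residual SD 4 | Type I error | k, residual SD 6 | Type I error |
|---|---|---|---|---|
| 0.25 | 1.14 | 6.6% | 1.06 | 5.7% |
| 0.5 | 1.51 | 11.1% | 1.24 | 7.8% |
| 0.75 | 2.05 | 17.1% | 1.51 | 11.1% |
| 1.0 | 2.64 | 22.7% | 1.86 | 15.0% |

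**Linear time, AR(1) errors, no slope variation.** Here k is the AR(1) variance of the standardised slope contrast over the average within-patient variance. Correlations 0.2, 0.3 and 0.5 give k = 1.35, 1.57 and 2.14, and errors of 9.2%, 11.8% and 18.0%.

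**Other forms of g(t).** The same comparison gives a weighted chi-square for the joint test of the time coefficients (large-sample, complete data, residual SD 4 for the slope columns; natural cubic splines with knots at 1, 4.5, 8 or at 1, 3.33, 5.67, 8).

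| Form of time | Slope SD 0.25 / 0.5 / 0.75 / 1.0 | AR(1) 0.2 / 0.3 / 0.5 |
|---|---|---|
| 3-knot spline | 5.9 / 8.7 / 12.6 / 16.7% | 9.7 / 12.7 / 19.1% |
| 4-knot spline | 5.6 / 7.4 / 10.3 / 13.4% | 9.5 / 12.1 / 17.3% |
| Categorical, 7-df joint test | 5.0 / 5.3 / 6.0 / 7.1% | 5.4 / 5.8 / 7.1% |

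At AR(1) 0.7 and 0.9 the categorical joint test reaches 8.7% and 10.4%. Within the categorical model, the week 1 versus week 8 contrast gives 5.8 / 8.1 / 11.4 / 14.9% over the four slope SDs.

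**Does it carry over?** Simulated with linear time at slope SD 0.5 and at AR(1) 0.5 (intercept and residual SD 4): β6 at n=120 gives 11.7% and 17.8%; β8 at n=130 gives 11.4% and 17.6%. The Protocol's continuation report has 99 completers of 138 enrolled (72%). With missing-at-random dropout leaving about 71% completers, β8 at n=120 gives 11.0% and 18.2%.

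**Omitted factors, as illustration only.** If conditions of equal size differ by d points per week, leaving condition out leaves slope SD d/2. At residual SD 4, d = 0.25, 0.5 and 1.0 give r = 0.031, 0.0625 and 0.125, and a β6 error of 5.4%, 6.6% and 11.1%. If WMH shifts the slope by 0.25 or 0.5 points per week per SD, the ED-only β8 test rejects in 6.8% or 10.8% of simulated trials.

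**The case against.** *The plan does not say that ε_ij is independent.* True: it writes the symbol and names the SAS procedure without its covariance statements. But it gives the random intercept as what handles the repeated measures and adds nothing else. An analyst following the text would fit that model.

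*The size has no anchor in the documents.* This stands. For linear time only the ratio of slope SD to residual SD matters, and it is unknown for HRSD and for expectancy. At slope SD 0.25 the excess is under two points. No single figure can be called the trial's error rate.

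*A reader might infer that the trial's own hypotheses guarantee leftover slope variation.* The documents do not support that. ED and WMH are also to be analysed in combination, and a model holding both removes that source. For the condition effect, the Protocol (Specific Aims and Hypotheses) reports that patients aged 60 or over in the preliminary study had no treatment benefit from the high- over the low-expectancy condition. A difference of 0.5 points per week would mean 7 × 0.5 = 3.5 points of divergence between weeks 1 and 8. Hypothesis 1 still allows larger condition effects in patients without ED or WMH, so this source may exist, at unknown size.

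*A reader might also infer that categorical time is safe.* It is nearly so for the joint test under moderate departures, but not under strong serial correlation. The week 1 versus week 8 contrast is more exposed, though the SAP offers such contrasts as aids to interpretation; the hypothesis test is β8.

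*The mediation test might seem to share the problem.* It is to be done "using the bootstrap method to obtain standard errors, confidence intervals, and the test for statistical significance", which is not affected in this way if whole patients are resampled.

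**Conclusion.** The point holds conditionally and should be fixed. With a random intercept as the only stated covariance, the tests of β8 and β6 hold 5% only if slopes do not vary beyond the modelled terms and weekly errors are uncorrelated. Otherwise their p-values are too small and their intervals too narrow. For linear time the true level is about 6.6% to 22.7% (residual SD 4) or 5.7% to 15.0% (residual SD 6) over slope SDs of 0.25 to 1.0, and about 9% to 18% for AR(1) of 0.2 to 0.5. Splines inflate less than linear time under slope variation and about as much under AR(1). The categorical joint test stays at about 5% to 7% for moderate departures and about 9% to 10% at AR(1) of 0.7 to 0.9. Which form applies is not known until BIC has chosen. These are mostly large-sample, complete-data figures on assumed variance components. They show what can happen, not what did. Confidence is medium for that reason.

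**What to change.** For Model 1 and the Aim 2 HRSD models, replace the random-intercept-only covariance with an unstructured residual covariance over weeks 1 to 8 and Kenward-Roger degrees of freedom. Pre-specify the fallback if it does not converge: correlated random intercept and slope plus AR(1) residuals. A random slope alone is not enough for spline time: under AR(1) of 0.2 to 0.5 it still gave 7.9% to 12.6%. Whenever the fallback is used, report patient-clustered standard errors with a small-sample correction as a sensitivity analysis. Do not use them for the 7-df categorical joint test, where they gave 7.1% to 8.1% at n=120 even when corrected.

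**Evidence.** At n=120 with complete data, the unstructured covariance gave 4.4% to 5.4% over all forms of time, with an exact growth-curve F test standing in for Kenward-Roger. The fallback gave 4.6% to 5.9% for linear and spline time. It was not run for categorical time, and neither option was run with dropout. The fallback is not exact for every shape: with exponential patient curves, splines keep about 6% to 7%.

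**Cost.** No new data, only changed covariance statements. Covariance parameters rise from 2 to 36 (8 × 9/2) for unstructured, or to 5 for the fallback. Intervals widen: with linear time and residual SD 4, the true standard error of β8 is √k = 1.07, 1.23, 1.43 and 1.62 times the random-intercept one over the four slope SDs. Apparent power falls accordingly.

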This project is designed to test the hypothesis that antidepressant response is lower in LLD patients with ED and WMH due to a loss of the component of medication response attributable to patient expectancy. Using a method of studying expectancy-based placebo effects emerging from my K23 Career Development Award,^{1,16,38} we will first assess participants at baseline using a neuropsychological test battery, anatomical MRI, and diffusion tensor imaging (DTI). Next, participants' expectancy of improvement will be manipulated by randomizing them to different probabilities of receiving the same antidepressant medication. The high expectancy condition is open escitalopram (i.e., 100% chance of receiving active medication), while the low expectancy condition is placebo-controlled administration of escitalopram (which participants believe represents 50% chance of receiving active medication). The difference in antidepressant response observed between the open and placebo-controlled medication treatments is a measure of the expectancy contribution to outcome, which is substantial in younger depressed adults but we hypothesize will be diminished in older patients with ED and/or WMH.

The finding that antidepressant non-response in LLD is caused by a disruption in expectancy effects would have several significant implications. Most importantly, understanding antidepressant non-response in LLD at the level of mechanism may permit the development of novel treatment interventions for patients with continued symptoms. For example, methods may be developed to restore the expectancy component of medication response through specific cognitive or manualized psychoeducational interventions aimed at

enhancing patients' expectation of improvement with antidepressant treatment. Pairing such interventions with inexpensive and widely available first-line antidepressant medications (i.e., SSRIs) may be a safe, feasible, and effective way to enhance treatment response. More speculatively, somatic treatments aimed at promoting prefrontal-limbic and prefrontal-striatal connectivity may be promising therapeutic avenues to explore. Such treatments might include drugs that augment neurotransmitters supporting frontostriatal circuitry (e.g., dopamine, acetylcholine) or transcranial magnetic stimulation (TMS).

Specific Aims and Hypotheses

Specific Aims and Hypotheses

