Specific Aim 1: To determine whether ED and/or WMH moderate the difference in patient expectancy and antidepressant outcome between the open vs. placebo-controlled conditions. Hypothesis 1: Greater ED and WMH will be associated with smaller differences in expectancy and antidepressant outcome between conditions.

Specific Aim 2: To determine whether a loss of expectancy effects mediates the relationship between ED/WMH and poor antidepressant outcome. Hypothesis 2: ED and WMH will be associated with decreased change in depressive symptoms, and these associations will be mediated by a decreased contribution of expectancy to antidepressant outcome.

Exploratory Aim: To assess the integrity of frontostriatal and frontolimbic white matter tracts using DTI and explore whether specific damage to these pathways is associated with diminished expectancy effects in patients with LLD.

Substantiating this model would provide a mechanism explaining how ED and WMH predict non-response to antidepressant medications in LLD. Understanding the mechanisms of antidepressant non-response in LLD has the potential to yield treatments based on specific and rational designs that target the involved biological pathways. By combining inexpensive and widely available antidepressant medications with psychoeducational interventions or targeted psychotherapies to enhance expectancy, it may be possible to significantly improve antidepressant response rates in LLD patients.

Description of Subject Population

Sample #1

Specify subject population

N=130 outpatients with MDD

Number of completers required to accomplish study aims

90

Projected number of subjects who will be enrolled to obtain required number of completers

130

Age range of subject population

60-90

Gender, Racial and Ethnic Breakdown

Gender: We anticipate the sample will be composed of approximately 60% women and 40% men.

Racial/ethnic group: On the basis of previous depression studies conducted in the Adult and Late Life Depression Clinic, it is anticipated that the sample will be composed of approximately 75% Caucasian, 15% African American, and 10% Hispanic subjects.

Description of subject population

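### Aim 2 mediation models omit randomised condition, a measured cause of expectancy that may also affect HRSD directly, so path b can be biased

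*SAP*

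**What the plan says.** - **Total effect (SAP, Analyses for Specific Aim 2).** The HRSD mixed model follows Model 1 but is fitted "only including predictors that do not involve randomized condition". This removes the condition main effect and every interaction with condition.
- **Path b (same section).** The same model is used again, with week 1 expectancy added as a predictor.
- **Path a (same section).** Week 1 expectancy is regressed on ED/WMH, controlling for baseline covariates. In Model 1 the covariate set is age plus any imbalanced baseline variables. That condition is absent here is read from this list; it is not stated as an exclusion.
- **Sensitivity analysis (same section).** It addresses unmeasured confounders of the mediation.
- **Intent (SAP, Overview).** Aim 2 asks whether "poor antidepressant outcome (regardless of randomized condition) is associated with more severe baseline ED and WMH burden", so pooling over conditions is deliberate.
- **Role of condition (Protocol, Background, Significance and Rationale).** "The difference in antidepressant response observed between the open and placebo-controlled medication treatments is a measure of the expectancy contribution to outcome".
- **Hypothesis 1 (Protocol, Specific Aims and Hypotheses).** "Greater ED and WMH will be associated with smaller differences in expectancy and antidepressant outcome between conditions".

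**The concern.** Mediation by expectancy requires that path b, the effect of week 1 expectancy on HRSD given ED/WMH, is free of common causes of expectancy and HRSD. Condition is assigned in order to move expectancy. It may also move HRSD in other ways. Under Study Procedures, open patients are told they are certain to receive the drug, while controlled patients are told that neither they nor their doctors know what they receive. Any effect of this on HRSD that does not pass through the week 1 expectancy score is credited to expectancy when condition is left out.

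If open treatment raises expectancy and also lowers HRSD by another route, the bias favours finding mediation. If the direct effect runs the other way, so does the bias. The Aim 2 conclusion rests on a*b, so a false or inflated path b feeds straight into it.

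A second, lesser issue is interpretation. Hypothesis 1 implies that the ED/WMH slope differs by condition. A single path a averages the two slopes and does not show where the mediation sits.

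**Working it through.** The documents as supplied give no effect size, SD or power for Aim 2, so there is no planned figure to reproduce. All effect sizes below are assumptions, in residual SD units.

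**Inputs from the SAP.** "All tests will be two-sided" at 0.05; open arm 60; double-blind "escitalopram-placebo trial (n=70, with n=60 to escitalopram and n=10 to placebo"; and "analysis for HRSD will drop the n=10 individuals who receive placebo". The HRSD set is therefore 60 + 60 = 120, and the expectancy set is 60 + 70 = 130.

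**1. Bias in path b.** Let d be the shift that condition produces in week 1 expectancy, and h its effect on HRSD by other routes. With 60/60 allocation the condition indicator has variance 0.25. Without condition, and with equal ED/WMH slopes, expectancy has residual variance v = 1 + 0.25d² given ED/WMH. The bias in b is 0.25dh/v.

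- d = 0.8, h = 0.5: v = 1.16, bias = 0.100/1.16 = 0.086.
- d = 0.5, h = 0.3: v = 1.0625, bias = 0.0375/1.0625 = 0.035.

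Simulation with a true b of -0.40 (path a 0.4 open, 0 controlled) agrees: -0.43 at d = 0.5, h = 0.3 and -0.50 at d = 1, h = 0.5. With condition in the model it is -0.40 in both.

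**2. False mediation when true b = 0.** Path a is 0.3 in both arms. As an approximation, both paths must be significant. SE(b) = √(1 + 0.25h²/v)/√(120v), and z for path a = 0.3√(120/v).

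- d = 0.8, h = 0.5: SE(b) = 0.087, bias/SE = 0.99, chance that b is significant 0.168; path a z = 3.05, power 0.86. Product: 0.168 × 0.86 = 0.145.
- d = 0.5, h = 0.3: SE(b) = 0.0895, bias/SE = 0.39, chance 0.068; path a z = 3.19, power 0.89. Product: 0.061.
- Condition adjusted: 0.05 × 0.91 = 0.045.

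Simulation with a bootstrap of a*b (60/60, 600 or 800 trials of 300 resamples, a single HRSD endpoint) gives:

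| d / h | As written | Condition adjusted |
|---|---|---|
| 0.8 / 0.5 | 15.5% (repeats 15.3%, 18%) | 6.5% (repeat 4%) |
| 0.8 / 0.3 | 8.0% | 5.5% |
| 0.6 / 0.3 | 6.5% | 4.7% |
| 0.5 / 0.3 | about 6% | about 6% |
| 0.5 / 0.2 | 5.7% | 5.8% |

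**3. Averaging in path a.** Let r be the controlled-arm slope divided by the open-arm slope. Pooled/open = (60 + 60r)/120.

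- r = 0: 0.50 (0.46 with 60/70).
- r = 0.25: 0.63.
- r = 0.5: 0.75.
- r = 1: 1.

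The z ratio of pooled to open-only path a is √2(1 + r)/2, which equals 1 at r = √2 - 1 = 0.41. With open path a 0.4 and b 0.3, simulated power for the indirect effect, pooled against open arm, is:

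- r = 0: 44% v 76%.
- r = 0.25: 62% v 74%.
- r = 0.5: 79% v 74%.
- r = 0.75: 83% v 74%.

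The crossover for a*b is lower if path b is also estimated in the open arm alone. With a = b = 0.4 and r = 0.25, power is then 0.74 pooled against 0.72 open.

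**The case against.** Pooling is a stated choice. Condition is randomised and so independent of baseline ED/WMH, which makes the pooled total effect and path a valid averages. That stands, but it does not protect path b: expectancy is not randomised, and condition is one of its causes. The question across conditions can still be answered with condition in the model.

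The bias may also be small. The Protocol reports an earlier study in which patients aged 60 or over showed little expectancy change and no benefit between conditions. HRSD raters are blinded, and open patients are told that some staff do not know their treatment. This argues against assuming large d and h, and the table shows near-nominal error when they are modest.

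Aim 1 already fits Model 1 to expectancy with condition interactions and week 1 contrasts, so the condition-specific effect on expectancy will be seen. What is not planned is carrying it into a*b.

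A reader might infer more than the documents support:

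- **That the controlled arm has little expectancy to lose, so pooling halves the effect.** Hypothesis 1 needs only a smaller slope there, not a zero one. The Protocol cites a large trial in which more severe WMH went with lower placebo response, which points to some effect where placebo is possible.
- **That pooling necessarily weakens the Aim 2 test.** Against the open-arm effect it loses power only when the controlled slope is below about 40% of the open slope; above that it gains.
- **That the open-arm effect should be the main result.** That would replace the stated question and use half the sample, after all interventions have been completed.

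**Conclusion.** The point holds for path b. As written, the Aim 2 models omit a measured variable that is designed to change the mediator and may affect the outcome by other routes, and the planned sensitivity analysis is not aimed at it. False mediation could be about 15% instead of about 5% under strong assumed shifts (0.8 SD on expectancy, 0.5 SD directly on HRSD). It stays near 6% for shifts of 0.5 and 0.3 SD or less. The documents do not say which case applies.

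Path a and the total effect are not confounded by condition. If Hypothesis 1 is true they understate mediation in the open arm by an amount that depends on r, which the documents do not give; one half is the limit at r = 0.

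The figures rest on single-endpoint linear models with 60 per arm, not the full mixed model, and ignore dropout. The correction is worth making because it is nearly free, not because large bias has been shown.

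**What to change.** 1. Add condition as a covariate to path a. In the Aim 2 HRSD model and path b, restore condition and condition x time (β3 and β5 of Model 1).
2. Keep the pooled indirect effect, now adjusted for condition, as the main Aim 2 result. It still answers the question across conditions.
3. As a secondary analysis, add condition x ED/WMH to path a and report the indirect effect in each condition with bootstrap intervals. Present it as estimation and note the lower precision. Do not make the open-arm effect the main result.
4. State whether the 10 placebo patients enter path a, given that Aim 1 keeps them for expectancy and drops them for HRSD.

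**Cost.** A few model terms on data already collected; the Protocol says only analysis is ongoing. If Aim 2 has already been run, report both fits. Adding condition hardly changes power. With equal slopes, one simulation gave 78% as written and 80% adjusted, and another 79% and 77%. The simulation standard error is about √(0.78 × 0.22/600) = 1.7 points. At r = 0 the figures are 44% and 45%.

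The by-condition results are less precise. With path a 0.3 in both arms, the open-arm effect has 54% power against 78% pooled. Power to show that path a differs by condition (together with path b) is about 0.57 at r = 0, 0.37 at r = 0.25 and 0.19 at r = 0.5, assuming a = b = 0.4.
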